8.1.1.5. Pregnancies

While pregnancy itself is not considered to be an AE or SAE, any pregnancy complication or elective termination of a pregnancy for medical reasons will be recorded as an AE or SAE as described in the protocol. If female subjects or female partners of male subjects become pregnant while on the study, the information will be included in the narratives.

8.2. Secondary Safety Analyses

8.2.1. Safety Analyses – Part 2

Safety measures described in Section 8.1 will comprise a secondary analysis for the Part 2 cohort and will be summarized and grouped by disease cohort.

8.2.2. Safety Analyses – Part 1 and Part 2

Safety tables will also be produced as a secondary analysis for all Part 1 and Part 2 patients combined as follows: 300 mg dose group (combining capsule and tablet cohorts), 400mg dose group, total RP2P dose group (combining those with 300 and 400 mg), and overall group (combining all Part 1 and Part 2 subjects of all dose levels). Food effect sub-study patients will be included with this summary.

8.3. Adverse Events of Special Interest Analyses

A comprehensive list of MedDRA terms based on clinical review will be used to identify each type of event.

• Selected adverse events include anemia, neutropenia, thrombocytopenia (platelet count decrease and thrombocytopenia), and fatigue.

Summaries of the number and percentage of subjects with these events will be provided for each type of events separately. The summary of event characteristics will also be provided, including number of subjects with any event, number of events, number of subjects with any event that is serious, number of subjects with any event that is related to study treatment, the outcome of the event, maximum grade and the action taken for the event. The percentage will be calculated in two ways, one with number of subjects with event as the denominator and the other with total number of subjects as the denominator. The worst-case approach will be applied at subject level for the event outcome and maximum grade, i.e., a subject will only be counted once as the worst case from all the events experienced by the subject. For action taken to an event, subject will be counted once under each action, e.g., if a subject has an event leading to both study treatment discontinuation and dose reduction, the subject will be counted once under both actions.

The onset and duration of the first occurrence of the selected adverse events will be summarized. This will include the number of subjects experiencing the event, the time of onset of the first occurrence of the event in days from first dose of study treatment, as well as the duration of the event in days.

In addition, summaries of adverse events and serious adverse events by preferred term will be provided specifically for bone-related events and ocular events.

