9.2. Time period and Frequency for collecting AE and SAE Information

- Any SAEs assessed as related to study participation (e.g., protocol-mandated procedures, invasive tests, or change in existing therapy) or related to a GSK product will be recorded from the time a subject consents to participate in the study up to and including any follow-up contact.
- AEs will be collected from the start of Study Treatment until the follow-up contact (see Section 8.2.2), at the timepoints specified in the Time and Events Table (Section 8.1).
- Medical occurrences that begin prior to the start of study treatment but after obtaining informed consent may be recorded on the Medical History/Current Medical Conditions section of the CRF.

- All SAEs will be recorded and reported to GSK within 24 hours of the investigator/site staff becoming aware of them, as indicated in Appendix 9.
- Investigators are not obligated to actively seek AEs or SAEs in former study subjects. However, if the investigator learns of any AEs or SAE, including a death, at any time after a subject has been discharged from the study, and he/she considers the event reasonably related to the study treatment or study participation, the investigator must promptly notify GSK.
- Post Protocol Amendment 8 implementation, for those subjects who continue to receive study treatment after DCO date of final analyses, the Sponsor will continue to collect safety information including SAEs, AESIs and AEs leading to treatment discontinuation via a paper process for up to 30 days after last dose of study treatment.

NOTE: The method of recording, evaluating and assessing causality of AEs and SAEs plus procedures for completing and transmitting SAE reports to GSK are provided in Appendix 9.

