15.6. Appendix 6: Derived and Transformed Data

15.6.1. General

Multiple Measurements at One Time Point

All data will be reported according to the nominal visit date for which it was reported (that is, no visit windows will be applied during dataset creation). Unscheduled data will only be included in the display sections that report most extreme result (e.g. worst grade post-baseline).

If multiple assessments on different days are reported for the same scheduled assessment, then the latest assessment for that scheduled assessment will be analyzed.

If multiple assessments are reported on the same date for the same scheduled planned time, then the worst-case result will be analyzed, with the exception of laboratory data reported from both central and local laboratories.

ECG values will be measured in triplicate: 3 assessments are collected for each scheduled planned time, the first 3 measures will be used to compute the mean values for ECG intervals at each scheduled planned time. For qualitative ECG measures (Normal, Abnormal, Not Clinically Significant, Abnormal, Clinically Significant) and QTcF grade, the most clinically significant value (highest grade) will be summarized.

Subjects having both High and Low values for Normal Ranges at any post-baseline visits for safety parameters will be counted in both the High and Low categories of "Any visit post-baseline" row of related summary tables.

Data from all assessments (scheduled and unscheduled), including multiple assessments, will be included in listings.

Study Day

Reference Dates

Unless otherwise stated, the safety reference (start) date will be the start of treatment of GSK3326595. This will also be the efficacy reference date for this study. The reference date for baseline characteristics (e.g. age) will be the date of screening.

Study Day for Safety Measures/Efficacy

If the date of interest occurs on or after the safety/efficacy reference date then the safety/efficacy study day will be calculated as (date of interest – safety/efficacy reference date) + 1. If the date of interest occurs before the safety/efficacy reference date then the safety study day will be calculated as (date of interest-safety/efficacy reference date). There is no safety/efficacy study day 0.

Duration of Elapsed Time

Durations (e.g., the duration of an AE, duration of exposure, etc.) are calculated as the stop date minus the start date plus one.

For elapsed time (e.g., the time since initial diagnosis):

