15.7.2. Handling of Missing Data

Element	Reporting Detail
General	 Missing data occurs when any requested data is not provided, leading to blank fields on the collection instrument : These data will be indicated by the use of a "blank" in subject listing displays. Unless all data for a specific visit are missing in which case the data is excluded from the table. Answers such as "Not applicable" and "Not evaluable" are not considered to be missing data and should be displayed as such. Missing data occurs when any requested data is not provided, leading to blank fields on the collection instrument Subjects with the designation of treatment relationship for adverse events (AE)s and serious adverse events (SAEs) missing will have the worst case assumed to be "Yes". There will be no other imputation for missing data other than what's described in Section 15.4.2. for partial dates and for missing exposure end dates.
Outliers	• Any subjects excluded from the summaries and/or statistical analyses will be documented along with the reason for exclusion in the clinical study report.
Responder Analysis	• For endpoints which determine the percentage of responders, subjects with unknown/not evaluable or missing best overall response will be assumed to be

Element	Reporting Detail
	non-responders, and will be included in the denominator when calculating the
	percentages.

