15.7.3. Handling of Missing and Partial Dates

Element	Reporting Detail
General	 Partial dates will be displayed as captured in subject listing displays. However, where necessary, display macros may impute dates as temporary variables for sorting data in listings only. In addition, partial dates may be imputed for 'slotting' data to study phases or for specific analysis purposes as outlined below. Imputed partial dates will not be used to derive study day, duration (e.g., duration of adverse events), or elapsed time variables (e.g., time since diagnosis). In addition, imputed dates are not used for deriving the last contact date in overall survival analysis dataset. With the exception of new anti-cancer therapy start date in the time to event analysis dataset and exposure end date in the exposure analysis dataset, imputed dates will not be stored on datasets.

Details on imputing partial dates for specific datasets are outlined below.

15.7.3.1. Adverse Events (AE):

Imputations in the adverse events dataset are used for slotting events to the appropriate study time periods and for sorting in data listings.

Dataset	Date	Missing Element	Rule	
Adverse Events (AE)	Start Date	day, month, and year	No Imputation for completely missing dates	
		day, month	If study treatment start date is missing (i.e. subject did not start study treatment), then set start date = January 1. Else if study treatment start date is not missing: If year of start date = year of study treatment start date then If stop date contains a full date and stop date is earlier than stud treatment start date then set start date = January 1. Else set start date = study treatment start date. Else set start date = January 1.	
		day	If study treatment start date is missing (i.e. subject did not start study treatment), then set start date = 1st of month. Else if study treatment start date is not missing: If month and year of start date = month and year of study treatment start date then If stop date contains a full date and stop date is earlier than study treatment start date then set start date= 1st of month. Else set start date = study treatment start date.	

Dataset	Date	Missing Element	Rule
			Else set start date = 1st of month.
	End		No imputation for partial end dates will be performed
	Date		

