3.20	All Treated	AE16	Summary of Serious Adverse Events by System Organ Class and Preferred Term (Number of Participants and Occurrences)	FDAAA, EudraCT Part 1 (by dose), Part 2 (by cohort), Part 1/Part 2 300mg/400mg/Total/Overall, Part 3 (by dose)	SAC
3.21	All Treated	AE1	Summary of Adverse Events Leading to Permanent Discontinuation of Study Treatment by System Organ Class and Preferred Term	IDSL Part 1 (by dose), Part 2 (by cohort), Part 1/Part 2 300mg/400mg/Total/Overall, Part 3 (by dose)	SAC
3.23	All Treated	AE3	Summary of Serious Adverse Events Related to GSK3326595 by Preferred Term	Part 1 (by dose), Part 2 (by cohort), Part 1/Part 2 300mg/400mg/Total/Overall, Part 3 (by dose) Please include a footnote describing how these events are selected (i.e. this table includes events for which the investigator selected as related to GSK only)	IA, SAC
3.24	All Treated	ESI2A	Summary of Onset and Duration of First Occurrence of Selected Adverse Events	Anemia, neutropenia, thrombocytopenia (platelet count decrease and thrombocytopenia), fatigue, Part 1 (by dose), Part 2 (by cohort), Part 3 (by dose)	SAC
3.25	All Treated	ESI1	Summary of Event Characteristics of Selected Adverse Events	Anemia, neutropenia, thrombocytopenia (platelet count decrease and thrombocytopenia), fatigue, Part 1 (by dose), Part 2 (by cohort), Part 3 (by dose)	IA, SAC
3.30	All Treated	DD1	Summary of Deaths	ICH E3 Part 1 (by dose), Part 2 (by cohort), Part 1/Part 2 300mg/400mg/Total/Overall, Part 3 (by dose) Report time to death from last dose (in days) as in the mock	SAC

No.	Population	IDSL / Example Shell	Title	Programming Notes	Deliverable
Labora	tory Results		•		
3.31	All Treated	LB1	Summary of Chemistry Changes from Baseline	ICH E3 To include grade increase from Baseline Grade Creatinine	SAC
3.32	All Treated	LB15	Summary of Worst-Case Chemistry Results by Maximum Grade Increase Post-Baseline Relative to Baseline	ICH E3 Report only worst-case post-baseline. Don't report by- visit summary rows. For CTCAE graded tests Part 1 (by dose), Part 2 (by cohort), Part 1/Part 2 300mg/400mg/Total/Overall, Part 3 (by dose)	SAC
3.33	All Treated	LB16	Summary of Worst Case Chemistry Results Relative to Normal Range Post- Baseline Relative to Baseline	ICH E3 Report only worst-case post-baseline. Don't report by- visit summary rows. For non-graded tests Part 1 (by dose), Part 2 (by cohort), Part 1/Part 2 300mg/400mg/Total/Overall, Part 3 (by dose)	SAC

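### As written, the AE duration summary in SAP 8.3 (Table 3.24) has no rule for events still ongoing, so it covers resolved first events only and is biased short

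*SAP*

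**What the plan says.** SAP 8.3 names four selected event types (anemia, neutropenia, thrombocytopenia, fatigue) and states: "The onset and duration of the first occurrence of the selected adverse events will be summarized". Both are to be given in days. The display is Table 3.24 in SAP 15.12.7, "Summary of Onset and Duration of First Occurrence of Selected Adverse Events". It is shown by dose in Parts 1 and 3 and by cohort in Part 2, for the final analysis.

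The rules that feed the table are elsewhere in the SAP:

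- Derivation, 15.6.1: "Durations (e.g., the duration of an AE, duration of exposure, etc.) are calculated as the stop date minus the start date plus one".
- AE end dates, 15.7.3.1: "No imputation for partial end dates will be performed".
- Use of imputed dates, 15.7.3: "Imputed partial dates will not be used to derive study day, duration (e.g., duration of adverse events), or elapsed time variables".
- Everything else, 15.7.2: "There will be no other imputation for missing data", apart from partial dates and missing exposure end dates.

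On when observation stops, Protocol 9.2 states: "AEs will be collected from the start of Study Treatment until the follow-up contact". Protocol 8.2.2 places the discontinuation visit within 30 days of the last dose.

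**The concern.** An event still present when observation ends has no stop date, so under these rules it has no duration and drops out of the duration statistics. Whether an event drops out depends on the quantity being measured, because a longer event is more likely to outlast its observation time. A mean or median over the remaining events describes events that resolved while observed. The table title presents it as the duration of the event.

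Unresolved events are foreseeable here. AE collection ends at the follow-up contact. Protocol 9.2.3 requires follow-up to resolution or stabilisation only for SAEs and for non-serious AEs of special interest. Protocol 9.1.2 defines the latter as ocular and bone-related events, so the four selected events, when non-serious, are not covered. Under Amendment 8, data collection ceases for subjects off treatment (Protocol 5.5). Subjects may also die with an event ongoing.

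At stake is how the report describes the persistence of these toxicities. Groups with different unresolved shares would be biased by different amounts, so their durations would not be comparable within the table.

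**Working it through.** The documents give no AE duration figure and no unresolved share, so there is no plan figure to reproduce. The check has three parts.

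**1. Applying the rules to an ongoing first event.** The start date is known and the stop date is blank. The 15.6.1 formula returns missing. 15.7.3.1 does not fill the end date, 15.7.3 would bar an imputed partial date from the duration, and 15.7.2 allows nothing further. An event whose stop date lacks only the day ends the same way. SAP 8.3 and the programming notes to Table 3.24 give no censoring date, cut-off substitution or count of ongoing events.

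The SAP does have such rules elsewhere. Duration of response follows the PFS censoring rules (7.2.6), and a missing exposure end date at an interim is replaced by the earliest of cut-off, withdrawal or death (15.7.3.5).

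**2. Direction.** Let D be the event's duration and C the time from onset to the end of observation, assumed independent. An event enters the table only if D ≤ C. The density of the durations that enter is proportional to f(t) × P(C ≥ t). The weight P(C ≥ t) falls as t rises, so the entering durations are shifted toward short values whatever the distribution of D.

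**3. Size, on assumed inputs.** If D is exponential with mean 1 and C is exponential with rate λ, the unresolved share is u = λ/(1+λ). D given D < C is then exponential with mean 1/(1+λ) = 1 − u. Mean and median both fall by the factor 1 − u. For u = 0.10, λ = 0.10/0.90 = 0.111 and 1/1.111 = 0.90, which is 10% short.

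That equality is special to the exponential. Simulated Weibull durations, with exponential or uniform observation times scaled to give the stated unresolved share, shorten the resolved-only median as follows:

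| Weibull shape | 10% unresolved | 40% unresolved |
|---|---|---|
| 0.7 | about 16–17% | about 57–58% |
| 1.0 | about 10% | about 40–43% |
| 1.5 | about 5% | about 24–27% |
| 2.0 | about 3% | about 15–18% |

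On a days scale, take exponential durations with a true median of 28 days and observation times uniform from 0 to L:

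| L (days) | Unresolved | Median, resolved only | Kaplan-Meier median |
|---|---|---|---|
| 60 | 52% | 12.5 | 27.9 |
| 120 | 32% | 18.4 | 27.9 |
| 240 | 17% | 23.1 | 28.0 |

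Across 27 such settings (shape 0.7, 1.0 or 1.5; true median 14, 28 or 56 days; L of 60, 120 or 240; 7% to 75% unresolved), the resolved-only median was below the truth every time. The smallest shortfall was about 4% (13.5 against 14 days) and the largest about 83% (9.3 against 56 days). Kaplan-Meier with unresolved events censored was within about 0.3 days of the truth throughout.

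**The case against.** **Exclusion is inferred.** No single sentence in the SAP says that ongoing events leave Table 3.24. It follows from the formula combined with the absence of any end-date rule. The table uses the standard shell ESI2A, which is not reproduced and might count or footnote ongoing events. This stands, and the conclusion is conditional on it.

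**Persistence is visible elsewhere.** Table 3.25 reports "the outcome of the event, maximum grade and the action taken for the event" for the same event types. Listing 10 shows all AEs, Table 3.35 gives worst-case haematology grades, and interruption durations are summarised (SAP 8.1.1.1). Protocol 8.3.5 asks for clinically significant abnormal laboratory values to be repeated until normal or back to baseline, which may reduce the unresolved share for the three cytopenias. These displays and rules help, but they do not repair the table. Table 3.25 takes the worst outcome across all of a subject's events, so it does not show how many first occurrences were unresolved. Repeat testing does not cover fatigue.

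**Unresolved does not mean longest.** An event that began shortly before observation ended is also unresolved. That is correct, and the statement is about tendency. The downward direction still holds.

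**A fixed floor.** A reader might infer that 10% unresolved guarantees about 10% bias. It does not: the median shortfall is about 5% at Weibull shape 1.5 and about 3% at shape 2.

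**Dose selection.** A reader might also infer that short durations affected the choice of dose. The documents do not support this. Protocol 4.3.2 mentions minimal cytopenias in connection with a PK/PD model, and it gives no cause for the dose reductions in 33 of 71 subjects. The dose decisions it describes (March 2018, and Amendment 4 in October 2019) precede the SAP of September 2022, and Table 3.24 is a final-analysis display.

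**Conclusion.** The concern holds for the duration statistics of Table 3.24. Under SAP 15.6.1, 15.7.2 and 15.7.3, a first occurrence without a complete stop date has no duration, and no other section supplies one. Unless shell ESI2A does otherwise, the table describes resolved events and understates duration.

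The direction rests only on observation time being unrelated to the event's own length. The size cannot be fixed from the documents. Under assumed Weibull shapes of 0.7 to 2, the median is short by about 3% to 17% with 10% unresolved and by about 15% to 58% with 40% unresolved.

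The consequence is limited to one descriptive safety table. Incidence, onset, the outcome rows of Table 3.25 and past dose decisions are not affected.

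**What to change.** In SAP 8.3 and the programming notes to Table 3.24:

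1. Show the number and percentage of first occurrences unresolved, by event type and group.
2. Estimate duration by Kaplan-Meier, with median and quartiles and 95% CIs. Censor events without a stop date at the earliest of death, end of AE collection, last contact or data cut-off. State censoring at death as an assumption, since death is a competing event.
3. Where a group is too small for a Kaplan-Meier median, give the number ongoing and label the durations as *resolved events only*.

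The cost is SAP wording and standard time-to-event code of the kind already planned for duration of response. No new data are needed. The downside is that the median may not be estimable in small dose groups: accelerated titration in Part 1 enrols one subject per level, and Part 3 about 10. Item 3 covers those groups.

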8.4. Clinical Laboratory Evaluations

Laboratory grades will be reported, where applicable, using the Common Terminology Criteria for Adverse Events (CTCAE v4.0), [Basch, 2014].

Summary of lab values and change from baseline by scheduled visits using mean, median, standard deviation, minimum and maximum will be provided.

Summaries of lab data by maximum toxicity grade will be provided for all the lab tests that are gradable by CTCAE v4.0.

Summaries of worst-case grade increase from baseline grade will be provided for all the lab tests that are gradable by CTCAE v4.0. These summaries will display the number and percentage of subjects with a maximum post-baseline grade increasing from their baseline grade. Any increase in grade from baseline will be summarized along with any increase to a maximum grade of 3 and any increase to a maximum grade of 4. Missing baseline grade will be assumed as grade 0. For laboratory tests that are graded for both low and high values, summaries will be done separately and labeled by direction, e.g., sodium will be summarized as hyponatremia and hypernatremia.

For lab tests that are not gradable by CTCAE v4.0, summaries of worst-case changes from baseline with respect to normal range will be generated. Decreases to low, changes to normal or no changes from baseline, and increases to high will be summarized at each scheduled visit as well as for the worst-case post-baseline. If a subject has a decrease to low and an increase to high during the same time interval, then the subject is counted in both the "Decrease to Low" categories and the "Increase to High" categories. In addition, the summary will include changes from baseline with respect to normal range by scheduled visits.

Separate summary tables for hematology, chemistry, urinalysis, troponin, and coagulation laboratory tests will be produced. A supporting listing of laboratory data for participants with any value outside the normal range will be provided. Troponin values outside the normal range, abnormal/clinical importance flag will also be provided.

Detailed derivation of baseline assessment is specified in Section 5.2.

Unless otherwise specified, the denominator in percentage calculation at each scheduled visit will be based on the number of subjects with non-missing value at each specified timepoint.

